9.0 Data Analysis

9.1 Statistical Hypothesis

[figure not shown]
The main hypothesis under investigation is that the incidence of sloughing over a 3-week period will be positively correlated with the level of SLS in the toothpaste assigned.

9.2 Sample Size Determination

A sample size of 72 represents a convenient sample size that should yield incidence rate estimates of adequate precisions to detect gross trends.

A sample size of 24 will give a precision (1/2 confidence interval width) of 4% if the observed incidence rate is 1%. Likewise, sample size of 48 will give precisions of 8.5-13% for incidence rates 10-30%, and a sample size of 72 will give precisions of 11.3-11.5% of incidence rates of 40-50%.

In addition, sample sizes of 72 and 48 will give 74% power to detect differences in proportions of 50% and 25%, respectively. Furthermore, sample sizes of 48 and 24 will give 77% power to detect differences in 25% and 1%, respectively using a two-sided Fisher's exact test with alpha of 0.05.

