4.6 Subject Withdrawal

Subjects may voluntarily withdraw from the study at any time without prejudice.

Any subject may be withdrawn by the Investigator from further participation in the study if the subject:

[figure not shown]
- Fails to adhere adequately to the protocol requirements within or outside the clinical environment
- Fails to cooperate adequately with the Investigator or staff during clinical visits
- Presents with an illness or disease condition that is not allowed in the study
- Experiences a serious AE that requires discontinuation or withdrawal from the study
- Experiences an intolerable AE
- Found not to meet the original entry requirements
- Fails to return for an appointment(s)
- Is pregnant

If a subject discontinues due to an AE (reported by the subject or the Investigator), the causative condition will be followed until resolution or stabilization to the Investigator's satisfaction.

Withdrawn subjects will not be replaced.

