8.0 Randomization

8.1 Randomization

Subjects will be numbered from 01 through 72. This number will be used to identify the subject on the case report forms. Subjects will be randomized in a 1:1:1 ratio into three different two-treatment sequences: (1) A-> C (2) B->C and (3) C->B. All seventy-two (72) subjects will be exposed to the high SLS toothpaste (C), 48 subjects will be exposed to the medium SLS toothpaste (B), and 24 subjects will be exposed to the no SLS toothpaste (A). See Appendix II for the randomization schedule.

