9.4.2 Secondary Analyses

The 95% confidence intervals will be computed for the sloughing rates for each treatment group using the Wilson score method. Significant trends in incidence rates across the treatment groups (from high to medium to no SLS toothpaste) will be tested using the Cochran Armitage test.

The oral mucosal sloughing index score will be used to compute the following two outcomes: (a) Overall subject-level incidence based on any non-zero score among the 12 oral areas examined, and (b) an average subject-level score based on the mean of 12 severity scores over all oral areas for each subject. These outcome scores will be summarized for each treatment group and if appropriate, will be analyzed using a generalized linear regression model such as a Poisson model to test for significant treatment, period and sequence effects.

The diary data will be used to compute treatment compliance with expected number of doses, and this will be summarized per period and treatment group.

Exploratory analysis may occur to examine the onset time and duration of adverse events.

The data collected on the subject acceptance questionnaire will be summarized by treatment group. If appropriate, these data will be analyzed for treatment differences using a generalized linear regression model such as an ordinal logistical model that takes into account the cross over design and the ordinal nature of the data.

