9.6 Procedures for Missing, Unused, or Spurious Data

Missing data due to subject withdrawals or subjects lost to follow-up will not be imputed. All data collected from each subject will be used in the statistical analyses.

[figure not shown]

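### The 4% precision stated for the 24-subject no-SLS group is a Wald half-width at a rate 24 subjects cannot show; the planned Wilson interval has a half-width of about 7–10%.

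*Combined protocol and SAP*

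**What the plan says.** Section 8.1 fixes the size of the reference group: "24 subjects will be exposed to the no SLS toothpaste (A"). Section 9.2 calls 72 a convenience number, says it should estimate incidence precisely enough to show broad trends, and then gives precisions for each group size:

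- n = 24: "A sample size of 24 will give a precision (1/2 confidence interval width) of 4% if the observed incidence rate is 1"%
- n = 48: "sample size of 48 will give precisions of 8.5-13% for incidence rates 10-30"%
- n = 72: "a sample size of 72 will give precisions of 11.3-11.5% of incidence rates of 40-50"%

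Section 9.2 names neither a confidence level nor an interval formula. Section 9.4.2 names both for the reported results: "The 95% confidence intervals will be computed for the sloughing rates for each treatment group using the Wilson score method".

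Two other provisions bear on the denominator. Section 4.6 says "Withdrawn subjects will not be replaced", and Section 9.6 says "Missing data due to subject withdrawals or subjects lost to follow-up will not be imputed".

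**The concern.** A half-width of 4% around 1% implies an interval from about −3% to 5%. The negative lower limit is a sign that the normal approximation has been used where it does not work: 24 × 0.01 is an expected count of 0.24 events. The plan does not intend to report that kind of interval, so Sections 9.2 and 9.4.2 disagree on how precise the no-SLS estimate will be.

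The no-SLS group is the smallest of the three and forms one end of the SLS trend that Section 9.1 sets out to show. Section 1.0 marks the study for safety use. A reader of Section 9.2 would expect a near-zero result in this group to exclude rates above about 5%. If the planned interval is much wider, a result with no sloughing at all would support a weaker statement than the plan suggests.

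**Working it through.** **Inputs.** n = 24, 48 and 72 with the rates and precisions in Section 9.2; 95% two-sided confidence and the Wilson method from Section 9.4.2; z = 1.96, z² = 3.8415.

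**Step 1: reproduce the plan's figures.** Wald half-width = z × √(p(1 − p)/n).

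| n | rate | Wald half-width | stated |
|---|---|---|---|
| 24 | 1% | 3.98% | 4% |
| 48 | 10% | 8.49% | 8.5% |
| 48 | 30% | 12.96% | 13% |
| 72 | 40% | 11.32% | 11.3% |
| 72 | 50% | 11.549% | 11.5% |

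All five match, which identifies the formula and confirms the 95% level. Other methods at n = 24 and 1% do not give 4%: Wald with continuity correction 6.1%, 90% Wald 3.3%, Wilson 7.7%, Wilson with continuity correction 9.3%, Clopper-Pearson about 8.0%, Agresti-Coull 9.9%.

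**Step 2: the planned interval at the same rate.** The Wilson interval has

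- centre = (p + z²/2n) / (1 + z²/n)
- half-width = z/(1 + z²/n) × √(p(1 − p)/n + z²/4n²)

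For n = 24, z/(1 + z²/n) = 1.96/1.1601 = 1.6895 and z²/4n² = 0.0016673. At p = 0.01 the half-width is 1.6895 × √(0.0004125 + 0.0016673) = 7.7%, with limits 0.06% and 15.5%. Like for like, 7.71/3.98 = 1.9.

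**Step 3: what 24 subjects can show.** The possible rates are 0, 1/24 = 4.17%, 2/24 = 8.33% and so on; 1% is not among them.

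- 0/24: the upper limit is z²/(n + z²) = 3.8415/27.8415 = 13.8%. The interval is 0–13.8%, half-width 6.9%.
- 1/24: the half-width is 1.6895 × √(0.0016638 + 0.0016673) = 9.75%. The interval is 0.7–20.2%.

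Against the stated 4%, these are 6.9/4 = 1.7 and 9.75/4 = 2.4 times as wide. The Wilson half-width is smallest when p(1 − p) = 0, so 6.9% is the minimum over all counts from 0 to 24. The Wald formula does not give 4% at the low counts either: it gives 0% at 0/24 and 8.0% at 1/24.

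**Step 4: average over a true rate of 1%.** P(0/24) = 0.99²⁴ = 78.6%, P(1/24) = 19.0%, P(2 or more) = 2.4%. Weighting the Wilson half-widths by these probabilities gives an expected half-width of 7.6%.

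**Step 5: the other group sizes.** Wilson half-widths are 8.69% and 12.56% for n = 48 at 10% and 30%, and 11.04% and 11.25% for n = 72 at 40% and 50%. The largest difference from Wald is 12.96 − 12.56 = 0.4 points. The fault is confined in practice to n = 24.

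**The case against.** The best reply is that nothing is miscalculated and nothing depends on the figure. Section 9.2 uses a standard planning approximation correctly. The sample size is declared to be one of convenience, and the paragraph goes on to give power as well as precision. The primary analysis in Section 9.4.1 is a logistic model with a Fisher fallback. The intervals are secondary, no success criterion uses a half-width, and because Wilson is prespecified the report will show the wider interval whatever Section 9.2 says. All of this is true. It limits the consequence, but the plan's own reporting method still contradicts the sentence.

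Three narrower points also have force:

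- The 2.4 multiple mixes two effects. At 1/24 the Wald half-width is already 8.0%, so the method alone accounts for 9.75/8.0 = 1.2 and the rest comes from the change of rate. The like-for-like multiple at 1% is 1.9.
- Some of the other stated rates are also unattainable: 10% and 30% of 48 are 4.8 and 14.4 subjects, and 40% of 72 is 28.8. Those lie within about one percentage point of an attainable rate, where little changes. At 1% of 24 the nearest results are 0% and 4.2%, and the interval differs materially between them.
- Half the width of a strongly asymmetric interval is not a plus-or-minus figure. The limits themselves describe the precision better, which is a reason to state them.

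**Conclusion.** The concern holds. The stated 4% is the Wald half-width at a rate that cannot be observed, and the Wilson method that the plan prescribes cannot produce it at n = 24. The attainable low results have half-widths of 6.9% (0/24) and 9.75% (1/24). With no sloughing at all in the group, rates up to 13.8% remain compatible with the data; with one case, up to 20.2%.

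This should be corrected. It does not threaten the primary test or the power statements, and it does not change the sample size. It is a roughly two-fold overstatement of precision for the reference group, in the section that uses precision to support the chosen size.

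The conclusion assumes that Section 9.2 refers to 95% intervals, as the match on all five stated figures indicates, and that all 24 subjects contribute. Withdrawals are neither replaced nor imputed, so the denominator can only fall and the interval at a given rate can only widen.

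**What to change.** In Section 9.2, replace the n = 24 sentence with the Wilson limits for the attainable results: 0 of 24 gives a 95% interval of 0–13.8%, and 1 of 24 gives 0.7–20.2%. State that the precisions are 95% Wilson half-widths, so that Sections 9.2 and 9.4.2 agree. Restate the rest on the same basis: 8.7–12.6% for n = 48 at 10–30%, and 11.0–11.3% for n = 72 at 40–50%. Describe those rates as planning values rather than observed ones.

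The cost is an edit to the two-sentence precision paragraph and a less favourable figure for the no-SLS group. No subjects, visits or analyses are added.

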9.3 Populations for Analysis

The datasets that will be used for the primary and secondary analyses including the adverse event analysis will include all subjects randomized into the study (intent-to-treat population). There will be no additional subset datasets defined for other analyses or sensitivity analyses.

9.4 Statistical Analyses

[figure not shown]
9.4.1 Primary Analyses

The primary endpoint is the incidence rate of sloughing. All sloughing clinically observed or subject-reported over the three-week treatment period will be recorded as an adverse event and coded using the MedDRA dictionary (with a preferred term of oral mucosal exfoliation). Differences in incidence rates will be tested for significance using a generalized logistic regression model that takes into account the crossover design with subject as a random effect and treatment, period, sequence and treatment-by-period interaction as fixed effects, non-significant treatment-by-period interaction effect will be dropped from the final model. In the event of failing convergence of the model or finding a significant treatment-by-period interaction (carry-over effect), the Fisher's Exact test maybe used to test for significant differences in sloughing rates among the treatment arms using all data or Period I data only, respectively.

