9.4.3 Adverse Event Analyses

Adverse event data will be coded using the MedDRA dictionary and the incidence rates will be summarized by preferred term and treatment group. Differences in incidence rates among the three groups will be tested using an overall Fisher's exact test and further pairwise testing (A vs B, A vs C and B vs C) will be carried out if the overall p-value is significant (<0.05).

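### The main hypothesis is an increase in sloughing with SLS level, but the primary analysis tests unordered differences and the only ordered test ignores pairing and period

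*Combined protocol and SAP*

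**What the plan says.** Section 9.1 gives one main hypothesis: "the incidence of sloughing over a 3-week period will be positively correlated with the level of SLS in the toothpaste assigned". It is ordered and has a direction.

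Section 9.4.1 sets the primary test: "Differences in incidence rates will be tested for significance using a generalized logistic regression model that takes into account the crossover design". The model has subject as a random effect and "treatment, period, sequence and treatment-by-period interaction as fixed effects". Treatment is not described as an ordered score, so with three toothpastes the natural reading is a factor tested on 2 degrees of freedom. The fallback is unordered too: "the Fisher's Exact test maybe used to test for significant differences in sloughing rates among the treatment arms".

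The ordered test is among the secondary analyses in 9.4.2: "Significant trends in incidence rates across the treatment groups (from high to medium to no SLS toothpaste) will be tested using the Cochran Armitage" test. Nothing there says that it allows for the crossover, whereas 9.4.1 and the questionnaire analysis in 9.4.2 both say so.

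Pairwise testing (A v B, A v C, B v C) is named only in 9.4.3, for adverse events, and only after a significant overall Fisher test. Sloughing is itself coded as an adverse event.

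Sections 3.1 and 8.1 allocate 72 subjects equally to A then C, B then C, and C then B. Every subject contributes two periods.

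**The concern.** A significant primary result would show that the three rates are not all equal. It would not show that they rise with SLS level: medium SLS could be the worst, or no SLS. The result that carries the trial's main claim would then come from a secondary test whose error rate is not the nominal 5%.

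That test has two faults in this design. It treats two responses from one person as two people. It also ignores period, although toothpaste level and period are tied together: A is given only in Period 1, and 48 of the 72 exposures to C fall in Period 2. A general rise in sloughing on the second exposure to the rinse would look like an SLS gradient, and a general fall would hide one.

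**Working it through.** **1. The plan's own power figures.** Section 9.2 uses a two-sided Fisher's exact test at 0.05. Enumerating two independent binomials, with 0.025 in each tail:
- C v B, 50% (n=72) v 25% (n=48): 74.2%; stated 74%.
- B v A, 25% (n=48) v 1% (n=24): 77.6%; stated 77%.

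Both reproduce. They concern two pairwise comparisons, not the overall model test or a trend. They imply planning rates of 1/25/50% for no/medium/high SLS.

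**2. Can the primary test be significant against the hypothesis?** At assumed rates of 10/30/20%, the unordered test in the crossover model rejects in about 42–45% of simulated trials and a trend test in about 4%. Taking the groups as independent gives 41% v 4%. Using only within-subject differences, with correlation 0 to 0.5, gives 21–38% v about 5%.

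**3. Size of the Cochran-Armitage test.** Period 1 has 24 A, 24 B and 24 C; Period 2 has 24 B and 48 C. With scores 0, 1, 2:
- Mean score = (24×0 + 48×1 + 72×2)/144 = 4/3, so the deviations are −4/3 (A), −1/3 (B) and +2/3 (C).
- The statistic is T = Σ(deviation × response). The test takes its variance as p(1−p) × (24×16/9 + 48×1/9 + 72×4/9) = 80p(1−p).

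*Pairing.* The product of a subject's two deviations is −8/9 for A–C and −2/9 for B–C or C–B. Their sum is 24×(−8/9) + 48×(−2/9) = −32. If the binary responses have within-subject correlation ρ, the true variance is p(1−p)(80 − 64ρ), and the size is 2Φ(−1.96/√(1 − 0.8ρ)).

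| ρ (assumed) | Size by formula | Simulated, 30% rate |
|---|---|---|
| 0.1 | 4.1% | 4.4% |
| 0.3 | 2.5% | 2.7% |
| 0.5 | 1.1% | 1.2% |

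If the correlation is set on a latent scale at 0.3–0.5, the simulated size is 2.6–3.5%.

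*Period.* The deviations sum to 48×2/3 − 24×1/3 = +24 in Period 2 and to −24 in Period 1. With no toothpaste effect and a Period 2 rate higher by d, the mean of T is 24d.
- d = 0.15 (30% to 45%): the mean of T is 3.6, the assumed SD is √(80×0.375×0.625) = 4.33, and the shift is 0.83 SD. The chance of exceeding 1.96 is about Φ(−1.13) = 13% under independence. Latent within-subject correlation of 0.3–0.5 brings it to about 9–10.5% in simulation.
- d = 0.05: the shift is 1.2/√(80×0.325×0.675) = 1.2/4.19 = 0.29 SD, and the size is about 6% even under independence.

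The excess therefore needs a sizeable period effect. The documents give no estimate of one.

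**4. Power, unordered 2-df test v 1-df score.** All rates except the first row are assumed.

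| Rates no/medium/high | 2-df | 1-df | Basis |
|---|---|---|---|
| 1/25/50% | 98.0%; 99.6% | 99.2%; 99.9% | within-subject, correlation 0; 0.3 |
| 10/20/30% | 35%; 47%; 61% | 44%; 57%; 71% | within-subject, correlation 0; 0.3; 0.5 |
| 10/20/30% | 48% | 58% | mixed-model simulation |
| 10/25/40% | 62% | 72% | within-subject, correlation 0 |
| 10/25/40% | 80% | 88% | mixed-model simulation |
| 5/30/30% | 34% | 30% | within-subject, correlation 0 |
| 5/35/35% | 75–79% | 53–56% | crossover-model simulation |

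**5. False positives when all rates are equal.** The overall test rejects in about 5% of trials. Three pairwise tests without a gate give at least one rejection in about 9–14%, depending on the test. With an overall gate, as in 9.4.3, the figure is 4.8–5.0%.

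**The case against.** A reader might infer three stronger things, and the documents support none of them.

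*That the hypothesis is never tested.* Section 9.4.2 prespecifies a trend test across the three levels. The fault is in its rank and its construction.

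*That the plan inflates false positives.* Section 9.4.1 names no pairwise contrasts. The only section that does, 9.4.3, gates them, and that gate covers sloughing as an adverse event. The 9–14% belongs to a procedure that nobody has planned. What remains is a silence: 9.4.1 does not say whether contrasts follow the model, although 9.2 is sized on two of them.

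*That the unordered test costs power in general.* At the plan's own rates the cost is about 1 point or less. The larger gains come from evenly spaced rates, the pattern that suits a 0/1/2 score best. A plateau also rises with SLS and then levels off, so the hypothesis does not exclude it, and there the score test is the weaker one. A further simulation at 5/35/35% gave 88% v 56% without the sequence term and 71% v 43% with it.

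Two other objections stand. A two-sided score test also rejects when the order is reversed (86–91% of runs at an assumed 40/25/10%), so the sign must be part of the rule. And for a safety study of convenience size, an overall test with rates, intervals and a trend test is a recognisable layout. But 9.2 justifies that size by the wish to detect gross trends, which itself points to an ordered test.

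**Conclusion.** The concern holds as a misalignment. The primary analysis does not target the ordered hypothesis in 9.1, and the one analysis that does has the wrong error rate in this design. It is too low when responses are correlated within subject (2.6–3.5% at latent correlations of 0.3–0.5) and too high when there is a sizeable period effect (about 9–10.5% at 15 points). The correlations, the period effect and the 10/30/20% pattern are assumptions. The direction of both errors follows from the allocation itself.

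Power is not the main argument. The ordered test gains about 8–13 points for weaker, evenly spaced trends (about 5–17 across the approximations tried). On a plateau it loses between 4 and about 30 points, depending on the rates and the model. The recommendation is worth making but is not critical, and it carries no claim that the plan as written inflates false positives through pairwise testing.

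**What to change.** In 9.4.1:
- Test the main hypothesis with a single 1-df SLS score (none 0, medium 1, high 2) in the crossover logistic model, with subject as a random effect and period as a fixed effect.
- Say whether the sequence term stays. It affects power, as the plateau runs show.
- State that support for the hypothesis needs a significant and positive slope.
- Report the odds ratio per SLS level with a 95% confidence interval, and the model-based rate for each toothpaste.
- Keep the 2-df treatment test as a prespecified supporting test, to reveal plateau or non-monotone patterns.
- If pairwise contrasts from the model are to be reported, say so and gate them on an overall test, as 9.4.3 does.

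In 9.4.2, let the model-based score test replace Cochran-Armitage. Moving Cochran-Armitage up unchanged would carry its error-rate problem into the primary analysis.

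The cost is wording only, with no extra subjects or data. The price is lower power for the primary test if sloughing levels off between medium and high SLS; the retained 2-df test covers that case.

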5.0 Study Materials

5.1 Description

- 3M Oral Rinse: The principle components of the 3M Oral Rinse being used in this study are described in Section 1.0 of this document and are the same for all treatment arms being used in this study. 15mL of 3M Oral Rinse will be swished for about 30 seconds twice a day (morning and evening), after brushing teeth with assigned toothpaste, for each 3-week treatment arm.

- Treatment A consists of a no SLS containing toothpaste. For the study, subjects randomized to Treatment A will receive 1 tube of Sensodyne ProNamel Fresh Breath toothpaste. The information on the components of Sensodyne toothpaste are listed on the packaging and safety data sheet.
- Treatment B consists of a medium SLS containing toothpaste. For the study, subjects randomized to Treatment B will receive 1 tube of 3M ESPE Clinpro Tooth Creme toothpaste. The information on the components of 3M Clinpro toothpaste are listed on the packaging and safety data sheet.
- Treatment C consists of a high SLS containing toothpaste. For the study, subjects randomized to Treatment C will receive 1 tube of Colgate Cavity Protection toothpaste. The information on the components of Colgate toothpaste are listed on the packaging and safety data sheet.

Subjects will be randomized to take two treatment products in sequence: either A followed by C, B followed by C, or C followed by B. Each of the treatments will be used in combination with the 3M Oral Rinse.

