6.2 Schedule of evaluations

Procedure	Visit 1 Period 1 Baseline	Visit 2 Period 1 Mid-Treatment Evaluation	Visit 3 ^a Period 1 End of Treatment	Visit 4 Period 2 Baseline	Visit 5 Period 2 Mid-Treatment Evaluation	Visit 6 Period 2 End of Treatment/ End of Study
	Day 0	Day 10 (±2 day)	Day 21 (±2 day)	Day 28+ (±2 day)	Day 38+ (±2 day)	Day 49+ (±2 day)
Informed Consent	X					
Eligibility	X					
Demographics	X					
Dental Exam	X	X	X	X	X	X
Dental Photographs		X ^b	X ^b	X ^b	X ^b	X ^b
Randomization	X					
Dispense 3M Oral Rinse	X			X		
Dispense Toothpaste	X			X		
Dispense Diary	X			X		
Questionnaire			X			X
Assess AEs		X	X	X	X	X
Diary collection			X			X
3M Oral Rinse collection			X			X

^a All subjects will complete a minimum of 1-week wash out with Treatment A between Visits 3 and 4.

^b Dental photographs are taken at the discretion of the Dental Examiner to capture sloughing and/or other abnormalities.

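### With sequence in the primary model, the treatment-by-period (carry-over) test has zero degrees of freedom, so the rule to drop the term or switch to Period 1 data has no valid trigger

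*Combined protocol and SAP*

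**What the plan says.** Section 5.1 has subjects take two toothpastes in order, "either A followed by C, B followed by C, or C followed by B", and section 8.1 allocates the three sequences 1:1:1. Toothpaste A (no SLS) is therefore a study treatment in Period 1 only.

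Section 9.4.1 analyses sloughing incidence with a logistic model "with subject as a random effect and treatment, period, sequence and treatment-by-period interaction as fixed effects". Two decisions follow from the interaction test. First, a "non-significant treatment-by-period interaction effect will be dropped from the final model". Second, on "finding a significant treatment-by-period interaction (carry-over effect"), Fisher's exact test may be applied to Period 1 data alone. A separate rule in the same sentence covers non-convergence (Fisher's exact test on all data).

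Section 9.3 says: "There will be no additional subset datasets defined for other analyses or sensitivity analyses". Section 9.4.2 plans models for the sloughing index outcomes "to test for significant treatment, period and sequence effects". The design safeguards against carry-over are the washout in section 6.2 ("All subjects will complete a minimum of 1-week wash out with Treatment A between Visits 3 and 4") and a dental examination at Visit 4.

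**The concern.** A two-period design with three sequences has few cells, and the primary model asks for four fixed-effect terms. If the first three terms already describe every cell, nothing is left with which to test the fourth. Yet the plan uses that fourth term to decide which analysis is primary. Either no p-value exists, or the software produces one by fitting the terms in an order that gives the interaction a df belonging to sequence. In the second case, a chance difference between randomised groups could be labelled carry-over and lead to all Period 2 data being set aside.

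**Working it through.** **Inputs.** Sequences and 1:1:1 allocation: sections 3.1, 5.1 and 8.1. Appendix II counts to 24 subjects on each sequence. Model terms and decision rule: section 9.4.1. The plan gives no df or other figure for the interaction, so there is no stated value to reproduce.

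**Step 1: the cells.**

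| | Period 1 | Period 2 |
|---|---|---|
| Sequence 1 | A | C |
| Sequence 2 | B | C |
| Sequence 3 | C | B |

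There are 3 × 2 = 6 sequence-by-period cells, so at most six fixed-effect parameters can be estimated.

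**Step 2: rank of the fixed-effect design over the six cells.**

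| Terms (with intercept) | Rank |
|---|---|
| Treatment + period | 1 + 2 + 1 = 4 |
| Treatment + period + interaction | 5 |
| Treatment + period + sequence | 1 + 2 + 1 + 2 = 6 |
| All four terms | 6 |

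Given sequence, the interaction has 6 − 6 = 0 df. Without sequence it has 5 − 4 = 1 df: only B and C occur in both periods, so the one df compares B with C across periods. Adding sequence after the interaction then gives 6 − 5 = 1 df instead of 2, so the interaction's df lies inside the sequence space.

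**Step 3: the exact dependency.** With 0/1 indicators,

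(B × Period 2) = 0.5·(Period 2) − 0.5·(C) + 0.5·(Sequence 3).

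Cell by cell:
- A in Period 1: 0
- C in Period 2, sequence 1: 0.5 − 0.5 = 0
- B in Period 1: 0
- C in Period 2, sequence 2: 0.5 − 0.5 = 0
- C in Period 1, sequence 3: −0.5 + 0.5 = 0
- B in Period 2, sequence 3: 0.5 + 0.5 = 1

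The identity holds on the linear predictor, so the logistic link does not alter it. The random subject effect adds no fixed-effect column, and more subjects add no cells.

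**Step 4: what the 1-df test would measure.** Rearranged, Sequence 3 = 2·(B × Period 2) + C − Period 2. In a model without sequence, a pure shift of d log-odds in the sequence 3 group therefore appears as an interaction of 2d, with shifts of +d in the C coefficient and −d in the period coefficient. The interaction also misses one natural carry-over comparison, C in Period 2 after A versus after B, because both cells are the same treatment in the same period. Explicit first-order carry-over columns do not help: after treatment, period and sequence the rank stays at 6.

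**Step 5: numerical check.** In one simulated data set (24 per sequence, random-intercept logistic model), the likelihood-ratio statistic for the interaction was 0 with sequence fitted. Without sequence the same data gave 3.93 on 1 df, against a 5% critical value of 3.84. One data set illustrates the dependence on model specification; it does not estimate how often it occurs.

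**Step 6: what the switch would discard.** Period 1 alone leaves 24 subjects per toothpaste. C falls from 72 to 24, B from 48 to 24, and A stays at 24.

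**Step 7: precision, relevant only to the optional change.** This uses a linear approximation with 24 per sequence and an assumed within-subject correlation ρ, since the plan gives none. With sequence fitted, B − A is the difference between two within-subject differences, with variance 2 × 2(1 − ρ)/24 in units of the outcome variance. Reductions are from unrounded values.

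| ρ | B − A variance, with sequence | B − A variance, without | Reduction: B − A | C − A | C − B |
|---|---|---|---|---|---|
| 0 | 0.167 | 0.071 | 57% | 43% | 14% |
| 0.3 | 0.117 | 0.068 | 42% | 31% | 10% |
| 0.5 | 0.083 | 0.058 | 31% | 23% | 8% |
| 0.7 | 0.050 | 0.041 | 19% | 14% | 5% |
| 0.9 | 0.0167 | 0.0156 | 7% | 5% | 2% |

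**The case against.** The algebra is not in dispute; the case against concerns its consequences. Section 9.4.1 lists sequence before the interaction. Fitted in that order, the term is aliased, no p-value appears, the switch never fires, and an estimable model (treatment, period, sequence) remains. The switch is also worded as permitted, not required. If sequence were left out, the 1-df test would not be invalid merely because chance can trigger it: sequences are randomised, and alpha allows for chance. Finally, section 9.3 can be read as defining which subjects are analysed, and a Period 1 analysis still uses all 72.

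Part of this stands. The fault may pass silently, the treatment estimates need not be harmed, and 9.3 is better called ambiguous than flatly contradictory. But a silent failure still means that the stated carry-over check does nothing. A list of terms is not a fitting order, and section 9.4.1 fixes none. The 1-df version is not the model the plan specifies, and it cannot separate carry-over from a sequence-group difference. Permissive wording adds discretion to a trigger that is already undefined. Section 9.3 also rules out sensitivity datasets in terms that can fairly be read to cover Period 1 data alone.

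**Conclusion.** The concern holds. Under the model as written, the treatment-by-period test has exactly 0 df, and both decisions built on it in section 9.4.1 lack a test statistic. This needs no assumption beyond the three sequences, the two periods and the listed terms. It should be corrected because it determines which analysis is primary.

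The limits are clear. Treatment effects remain estimable once the redundant term is removed, and the washout and the Visit 4 examination still protect against carry-over by design. The non-convergence rule is separate and unaffected. It may matter in practice: at the 1% planning rate in section 9.2, the chance of no events among the 24 subjects on A is 0.99^24 = 0.786, about 79%. Ordinary maximum-likelihood log-odds contrasts with A would then not be finite, and the variance figures in the working would not apply.

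**What to change.** Required:
- In 9.4.1, delete the treatment-by-period term and the significance-triggered switch to Period 1 data, and prespecify one primary model without them.
- Report the randomised Period 1 comparison as a prespecified sensitivity analysis whatever the primary result, and amend 9.3 to allow it.

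Optional but preferred: also drop fixed sequence, leaving treatment and period with subject as a random effect. The model then relies on randomisation to balance the sequence groups, and 9.4.2, which plans sequence effects, should be aligned. Keeping treatment, period and sequence also cures the 0-df fault, at some loss of precision, mainly for contrasts with A when the within-subject correlation is low.

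If an interaction is inspected in a model without sequence, report it descriptively and state that its single df (B versus C across periods) cannot be separated from a sequence-group difference.

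The cost is text edits to 9.4.1 and 9.3, and to 9.4.2 if sequence is dropped. No new data or subjects are needed.
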